There is extensive preclinical and clinical data on this agent, which is FDA approved in adults with recurrent multiple myeloma at a dose of 20mg 3x/week x 2 weeks of a 3 week cycle⁷⁰.

In the present trial, we seek to evaluate this promising drug for use as a single agent in children with recurrent/progressive DIPG. The initial dose level we propose to use is approximately 80%

of the approved adult dose.

Rationale for Amendment 4:

We have enrolled 11 patients to date, 7 so far are evaluable (1 was inevaluable and 3 are still in the DLT period). Two patients enrolled onto dose level 1 and did not experience a DLT. The subsequent 6 patients were enrolled onto dose level 2. One patient experienced a dose limiting toxicity of grade 3 thrombocytopenia, and was dose reduced to level 1. One patient was inevaluable due to disease progression. A second patient experienced dose limiting toxicities of grade 4 thrombocytopenia and grade 4 neutropenia, and was dose reduced to level 1. Given 2 occurrences of DLTs at dose level 2, the subsequent 3 patients have been enrolled onto dose level 1. Should they tolerate dose level 1 (10mg/m²), it will be declared the maximum tolerated dose (MTD) for the 3 weeks on 1 week off schedule.

The recommended phase 2 dose has been identified for children with recurrent/progressive DIPG as 10 mg/m², and now we will evaluate panobinostat as a single agent in children with DIPG who have not yet progressed in a separate stratum (Stratum 2), using an alternative schedule. Given the limited BBB (blood brain barrier) penetration of panobinostat, it is highly desirable to maximize the dose administered as part of treatment. To improve the tolerability of panobinostat, we propose a new schedule of Monday, Wednesday, Friday dosing every other week. *In vivo* DIPG orthotopic xenograft data show prolonged duration of tumor suppression in mice treated with weekly 20mg/kg systemic panobinostat compared to mice treated 10mg/kg 3 times per week ⁵⁴, suggesting that higher doses administered less frequently may be more beneficial than lower doses administered more frequently. In addition to the change in dosing schedule, we will be studying DIPG patients prior to progression to avoid confusion between effects of tumor progression and putative toxicity of the agent. Furthermore, our plans for future efficacy studies focus on DIPG patients prior to progression in order to maximize the likelihood of success.

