Treatment may be administered on an outpatient basis. Reported adverse events and potential risks are described in Section 7. Appropriate dose modifications are described in Section 6. No investigational or commercial agents or therapies other than those described below may be administered with the intent to treat the patient's tumor.

5.1 *Agent Administration*

Patients with recurrent/progressive DIPG will be enrolled at the time of progression in Stratum 1. Therapy with panobinostat will be administered every other day, 3 times/ week, p.o. preferably on a Monday/Wednesday/Friday schedule for three weeks, followed by one week off of therapy. Three weeks of therapy plus the one week rest period (total 4 weeks) will constitute one course. Treatment will continue for up to 26 courses (approximately 2 years) barring progressive disease or unacceptable toxicity.

Patients with DIPG or H3K27M+ Thalamic DMG who have not progressed will be enrolled after receiving standard radiation therapy in stratum 2 and cannot begin treatment until at least 14 days after completion of radiation. Therapy with panobinostat will be administered every other day, 3 times/ week, every other week. **A minimum of 6 days without drug is required between treatment weeks.** Four weeks will constitute one course. Treatment will continue for up to 26 courses (approximately 2 years) barring progressive disease or unacceptable toxicity.

5.1.1 *Panobinostat*

Panobinostat will be provided by Secura Bio Inc. Oral panobinostat will be supplied as 5 mg, 10 mg, 15 mg orange colored, and/or 20 mg reddish colored opaque, hard gelatin capsules.

Subjects will be assigned a dose level at the time of enrollment. See Section 5.1.6 below for details of dose escalation schedule. See Section 6 for dose modifications.

Dosing should be adjusted based on BSA calculated at the beginning of each course of therapy. The dose prescribed should be rounded to the nearest deliverable dose based on the BSA adjustment and the available pill sizes. Dosing Tables which reflect this approach are available in **Appendix D: Dosing Tables**. Patients will be provided with a Medication Diary for panobinostat, instructed in its use, and asked to bring the diary as well as the remaining pill bottles with them to each appointment. The Patient Diary is available in

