7.3.7 NCI Guidance for Reporting Protocol Deviations

The site must enter all protocol deviations into the PBTC RAVE database. Participating centers must also submit the report to their IRB in accordance with their institutional policies. Protocol deviation data entered in the PBTC RAVE database will be imported periodically to the NCI Protocol Support Office.

8 Agent Information

A list of the adverse events and potential risks associated with the investigational agent administered in this study can be found in Section 7.1.

8.1 *Panobinostat*

Chemical Name: 2-Hydroxypropanoic acid, compd. with 2(E)-N-hydroxy-3-[4-[[2-(2-methyl-1H-indol-3-yl)ethyl]amino]methyl]phenyl]-2-propenamide (1:1)

Other Names: (LBH589-lactate); Farydak®

Classification: Histone Deacetylase (HDAC) Inhibitor

CAS Registry Number: 404950-80-7

Molecular Formula: C₂₁H₂₃N₃O₂·H₂O monohydrate

M.W.: 439.50416 g/mol

Mechanism of Action: May include effects on epigenetic mechanisms of gene expression as well as modulation of acetylation and function of histones

Formulation: Oral formulation: hard gelatin capsules contain panobinostat lactate salt at dosage strengths of 5 mg, 10 mg, 15 mg and 20 mg as anhydrous free base. The 5mg and 15mg capsules are packaged in high-density polyethylene (HDPE) bottles with an induction seal and plastic CR closure. The 10mg and 20mg formulations are packaged in blister packs with 6-ct capsules/pack. The 5 mg formulation will no longer be available after July 2021.

Storage: Store in a very tight packaging with water permeation <0.5 mg/day/liter, protect from light. Store below 25°C.

Stability: The shelf life for the capsule formulations is assigned based on ongoing stability studies.

Availability: Panobinostat capsules are provided by Secura Bio Inc.

Route of Administration: Capsules are to be taken orally by mouth and swallowed whole.

8.2 *Agent Ordering*

Panobinostat may be requested by the Principal Investigator or designees at each participating institution. All regulatory documents, as required by the PBTC, must be current and up to date prior to requesting the study drugs. Drug request form can be found on the PBTC-047 protocol and resources webpage under <https://www.pbtc.org/members/Protocols/protocols.htm>. The form can be emailed to [REDACTED] and [REDACTED] at [REDACTED] at Secura Bio Inc. (Phone number [REDACTED]).

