13.1.1 Proposed Dose Levels and BSA Based Dosing

Since panobinostat is an oral agent and supplied in fixed capsule sizes, the deliverable doses based on BSA considerations are limited to the rounding constraints as set by the minimum capsule size. Taking this into consideration along with the starting dose of 10mg/m² in Stratum 1 we developed an algorithm that enabled us to choose dose levels that would avoid overlaps in BSA adjusted doses in our patient cohorts. The following plot illustrates the BSA adjusted doses that the patients would receive at the proposed dose levels based on a minimum capsule size of 5mg. For the lower dose levels we have also utilized minimum BSA restrictions for enrollment to avoid these overlaps. Dosing nomograms are provided in **Appendix D: Dosing Tables** to facilitate correct dosing of patients based on this approach.

Figure 2: BSA Adjusted Doses vs. Body Surface Are for the Proposed Dose Levels

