Appendix D: Dosing Tables

5 mg/m² (Patients with BSAs <0.8m ² are not eligible to be treated at this dose)					
Min BSA (m²)	Max BSA (m²)	Daily panobinostat Dose (mg)	Min BSA (m²)	Max BSA (m²)	Daily panobinostat Dose (mg)
0.80	1.49	5	1.50	2.5	10
10 mg/m² (Patients with BSAs <0.65m ² are not eligible to be treated at this dose)					
Min BSA (m²)	Max BSA (m²)	Daily panobinostat Dose (mg)	Min BSA (m²)	Max BSA (m²)	Daily panobinostat Dose (mg)
0.65	0.78	5	1.75	2.25	20
0.79	1.25	10	2.26	2.50	25
1.26	1.74	15			
16 mg/m² (Patients with BSAs <0.65m ² are not eligible to be treated at this dose)					
Min BSA (m²)	Max BSA (m²)	Daily panobinostat Dose (mg)	Min BSA (m²)	Max BSA (m²)	Daily panobinostat Dose (mg)
0.65	0.78	10	1.72	2.03	30
0.79	1.09	15	2.04	2.34	35
1.10	1.40	20	2.35	2.5	40
1.41	1.71	25			
22 mg/m² (Patients with BSAs <0.65m ² are not eligible to be treated at this dose)					
Min BSA (m²)	Max BSA (m²)	Daily panobinostat Dose (mg)	Min BSA (m²)	Max BSA (m²)	Daily panobinostat Dose (mg)
0.65	0.78	15	1.71	1.93	40
0.79	1.02	20	1.94	2.15	45
1.03	1.24	25	2.16	2.38	50
1.25	1.47	30	2.39	2.50	55
1.48	1.70	35			
28 mg/m² (Patients with BSAs <0.50m ² are not eligible to be treated at this dose)					
Min BSA (m²)	Max BSA (m²)	Daily panobinostat	Min BSA (m²)	Max BSA (m²)	Daily panobinostat

		Dose (mg)			Dose (mg)
0.50	0.62	15	1.52	1.69	45
0.63	0.78	20	1.70	1.87	50
0.79	0.98	25	1.88	2.05	55
0.99	1.16	30	2.06	2.23	60
1.17	1.33	35	2.24	2.41	65
1.34	1.51	40	2.42	2.50	70
36 mg/m²					
(Patients with BSAs <0.50m² are not eligible to be treated at this dose)					
Min BSA (m²)	Max BSA (m²)	Daily panobinostat Dose (mg)	Min BSA (m²)	Max BSA (m²)	Daily panobinostat Dose (mg)
0.5	0.62	20	1.60	1.73	60
0.63	0.76	25	1.74	1.87	65
0.77	0.90	30	1.88	2.01	70
0.91	1.04	35	2.02	2.15	75
1.05	1.18	40	2.16	2.29	80
1.19	1.31	45	2.30	2.43	85
1.32	1.45	50	2.44	2.50	90
1.46	1.59	55			

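### Two Appendix D rows need 5 mg capsules that end after July 2021, with no substitute dose stated; under the 5.1.1 rounding rule some one-level reductions would leave the milligram dose unchanged

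*Combined protocol and SAP*

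**What the plan says.** - **Section 8.1 (Formulation):** "The 5 mg formulation will no longer be available after July 2021". The 10, 15 and 20 mg strengths are not withdrawn.
- **Section 5.1.1, supply:** "Oral panobinostat will be supplied as 5 mg, 10 mg, 15 mg orange colored, and/or 20 mg reddish colored opaque, hard gelatin capsules". Capsules must be swallowed whole, so 5 mg cannot be made from a larger capsule.
- **Section 5.1.1, rounding:** "The dose prescribed should be rounded to the nearest deliverable dose based on the BSA adjustment and the available pill sizes". The next sentence points to the Appendix D tables as reflecting this approach.
- **Section 13.1.1:** the algorithm was built to "choose dose levels that would avoid overlaps in BSA adjusted doses in our patient cohorts", and the plotted doses are "based on a minimum capsule size of 5mg". Minimum BSA limits at the lower levels serve the same purpose.
- **Appendix D:** 5 mg is still tabulated at 10 mg/m² for BSA 0.65-0.78 and at 5 mg/m² for BSA 0.80-1.49. Patients below a level's minimum BSA "are not eligible to be treated at this dose".
- **Section 6.2:** after a hematologic DLT that resolves in time, a patient may resume one dose level lower. Each patient may have only one reduction. Tables 13 and 14 also call for reductions in stated cases. Section 6.1 requires the study chair or co-chair to be told beforehand.
- **Section 13.2 (version 8 update):** Stratum 2 level 3 was too toxic, de-escalation to level 2 (22 mg/m²) had begun, and further de-escalation to level 1 is foreseen.

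**The concern.** The end of the 5 mg strength appears in one section and was not carried into the dosing rule, the dose-level rationale or the tables. A site that needs one of the two 5 mg rows after July 2021 has a printed dose it cannot dispense and a rounding rule that leads to 10 mg.

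For a child at BSA 0.65-0.78 reduced from 16 to 10 mg/m², that 10 mg is the dose already being taken. The child could restart after dose-limiting toxicity on the same milligram dose, recorded as a reduction, and the single reduction in Section 6.2 would be used up. Levels are defined in mg/m², so the wording on dropping one level does not itself rule this out. Notice to the chair is a check, but it does not say what dose to give.

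**Working it through.** **Inputs.** All 50 Appendix D rows; capsule strengths and the end of the 5 mg strength (8.1); the rounding rule (5.1.1); one-level reductions (6.2). Assumption: the 10, 15 and 20 mg capsules remain available.

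**1. Reproduce the plan's tables.** Each level × BSA was rounded to the nearest dose deliverable from 5, 10, 15 and 20 mg capsules, in BSA steps of 0.01 m² from each level's minimum to 2.50. This matches Appendix D at 1125 of 1131 points. The six exceptions lie at band edges: 10 mg/m² at 0.76-0.78, 22 mg/m² at 0.79, and 28 mg/m² at 0.79-0.80. In the first, 7.6-7.8 mg is nearer 10 mg, but the table gives 5 mg, which keeps the level below the 10 mg given at 16 mg/m². With 5 mg capsules, no one-level step in Appendix D leaves the dose unchanged.

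**2. Remove the 5 mg capsule.** Sums of 10, 15 and 20 mg give 10, 15, 20, 25 mg and so on. Only 5 mg is lost, which affects 2 of 50 rows.

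**3. Keep the Appendix D bands and replace 5 mg by the nearest deliverable dose, 10 mg.**

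| Step (mg/m²) | BSA (m²) | Upper level | Lower level | Tabulated | Without 5 mg |
|---|---|---|---|---|---|
| 16 to 10 | 0.65-0.78 | 10.4-12.48 mg | 6.5-7.8 mg | 10 to 5 mg | 10 to 10 mg |
| 10 to 5 | 0.80-1.25 | 8.0-12.5 mg | 4.0-6.25 mg | 10 to 5 mg | 10 to 10 mg |
| 10 to 5 | 1.26-1.49 | 15 mg (table) | 5 mg (table) | 15 to 5 mg | 15 to 10 mg |

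At BSA 1.25 the 12.5 mg tie is settled as 10 mg by Appendix D. The 22-to-16, 28-to-22 and 36-to-28 steps are never unchanged.

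**4. Delivered dose.**
- 10 mg/m² level, BSA 0.65-0.78: 10/0.78 = 12.8 to 10/0.65 = 15.4 mg/m², against 5/0.78 = 6.4 to 5/0.65 = 7.7 as tabulated.
- 5 mg/m² level, BSA 0.80-1.25: 10/1.25 = 8.0 to 10/0.80 = 12.5 mg/m².
- 5 mg/m² level, BSA 1.26-1.49: 10/1.49 = 6.7 to 10/1.26 = 7.9 mg/m², still a cut of (15 − 10)/15 = 33%.

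**5. How likely is the 16-to-10 step?** Section 2.4 reports two DLT patients at 16 mg/m² in Stratum 1: "One patient experienced a dose limiting toxicity of grade 3 thrombocytopenia, and was dose reduced to level 1"; "A second patient experienced dose limiting toxicities of grade 4 thrombocytopenia and grade 4 neutropenia, and was dose reduced to level 1". Six were enrolled there and one was inevaluable, so 2 of 5, with BSA not given. That schedule has 9 doses per course; Stratum 2 has 6. In Stratum 2, 3 patients were treated at level 1 and the trial went on to level 3. Section 13.1.2 bars assignment above a level with a DLT rate of 33% or more, and 1/3 = 33.3% would have blocked escalation. If the rule was followed, there were 0 course-1 DLTs among those 3. De-escalation to level 1 would call for treating up to 12 patients there, so about 12 − 3 = 9 more.

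**6. Timing.** The text cites a brochure dated 12 March 2020, taken here as the earliest date of the text. Up to 70 − 47 = 23 further patients at 1-2 per month take 11.5-23 months, so accrual could end between about February 2021 and February 2022. Treatment can run for 26 courses. Dosing after July 2021 is plausible but not stated.

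**The case against.** **Appendix D is the operative table.** Section 5.1.1 points to it and Section 13.1.1 says it is there to support correct dosing. A site following it meets a 5 mg dose it cannot dispense; reaching 10 mg means giving twice the printed dose. This stands, and it sets the order of the problem: first an undeliverable dose, and an unchanged dose only if the site turns to the rounding rule. A reader might infer that the protocol instructs sites to restart a child at the toxic dose. It does not: Section 6.2 permits resumption only one level lower, and Section 5.3.2 lets the physician stop. But nothing states what replaces the missing dose.

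**The Stratum 1 experience overstates the risk.** A reader might carry the 2 of 5 over to Stratum 2. The denser schedule and the implied 0 of 3 argue against that, although 3 patients in one course is little evidence either way.

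**The 10-to-5 step is remote.** This stands. With one reduction per patient, nobody assigned 22 or 16 mg/m² can reach it. It needs a patient assigned 10 mg/m²: two further trial-level de-escalations, or a Stratum 1 patient still on drug after July 2021.

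**Stopping therapy is a hard rule in a fatal disease.** Section 5.1.6 aims to keep patients on drug, and a mandatory stop is only one acceptable answer. This stands, and the fix leaves room for another real reduction.

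**Conclusion.** The conflict is in the current text and should be corrected. After July 2021, 2 of 50 Appendix D rows cannot be dispensed. Under the 5.1.1 rule the dose stays at 10 mg for 16-to-10 at BSA 0.65-0.78 and for 10-to-5 at BSA 0.80-1.25.

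Reach is narrow. The main case is Stratum 2 de-escalated to 16 mg/m², with a child at BSA 0.65-0.78 who then needs a reduction. The active 22-to-16 step is unaffected. A reader might infer harm to the dose-finding result. At the levels version 8 foresees there is none: a DLT that triggers a reduction has already been counted at the assigned level, PK samples are taken on days 1 to 3 of course 1, and PFS is summarised by stratum. Nor do the documents show that any child was affected; they give no BSA distribution and no dosing counts by date.

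This rests on the other three strengths remaining available, on level 1 being 16 mg/m² as tabulated, and on the escalation rule having been followed.

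**What to change.** For dosing after July 2021:

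1. Correct the capsule list in Section 5.1.1 and the 5 mg minimum in Section 13.1.1.
2. Remove the 10 mg/m² row for BSA 0.65-0.78 and raise that level's minimum BSA to 0.79 in Appendix D, Tables 2 and 11, and Section 3.3.3.
3. Mark 5 mg/m² as not dispensable below BSA 1.26. At BSA 1.26-1.49, 10 mg is usable only as a reduction from 15 mg.
4. State in Section 6.2, applying also to Tables 13 and 14, that where a reduction is called for, a patient held for toxicity must not restart on the same milligram dose and schedule under a nominal one-level reduction. If no lower deliverable dose exists, the patient comes off protocol therapy unless the sponsor specifies another real reduction, such as fewer doses per course. The cases where those tables deliberately allow an unchanged dose stay as they are.

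The cost is amendment wording and a revised Appendix D, with no added patients or procedures. The downside is that a few small children become ineligible at 10 mg/m² or stop treatment after toxicity.

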9.2 Pharmacokinetics – Plasma (Required)

Plasma pharmacokinetic studies are mandatory and will be obtained from all patients enrolled on this study.

9.2.1 Collection of Specimens

Sampling Strategy for Pharmacokinetic Study (Note: Patients should take Panobinostat in a fasting state on Days 1 and 3 of Course 1 only)

- On Day 1 of Course 1, serial blood samples of 2 ml each for panobinostat pharmacokinetic studies will be collected at the following times: pre-dose and at 0.5, 1, 2, 4, 8 (± 1), and 24 (± 4) hours after the oral dose.
- On Day 3 of Course 1 (pre-dose 2), a single sample of 2 ml will be collected prior to the drug dose.

9.2.2 Handling of Specimens

At each time point, 2 ml of blood will be collected into appropriately labeled tubes containing Sodium Heparin. 2 ml of blood is needed to provide approximately 2 aliquots plasma for pharmacokinetic analysis. The Pharmacokinetic data collection form should be completed with the exact time that the sample is drawn as well as the exact time that the drug is administered. The PK data collection form is located on the PBTC-047 webpage.

[figure not shown]
During the sample collection and processing steps, the blood and plasma should be kept out of direct sunlight and unfiltered lab light. Upon collection of the blood PK samples in Na Heparin blood collection tubes, keep the blood samples on wet ice at all times prior to processing to plasma. Within 30 minutes of collection, samples will be centrifuged at approximately 2000 x g for about 10 minutes at 4°C (Note: If a refrigerated centrifuge is not available, please refer to the Shipping Manual located on the PBTC-047 webpage for further instructions). The plasma will be stored in an appropriately labeled amber screw-capped polypropylene tube and stored immediately at approximately -20°C.

9.2.3 Shipping of Specimens

Samples should be shipped for delivery Monday through Thursday with a generous amount of dry ice enclosed to safeguard against shipping delays. Weekend and holiday deliveries should be avoided. At the start of the study, each participating institution should refer to the PBTC-047 website for instructions to request a Pharmacokinetics Kit for each patient enrolled on the study.

Samples should be batched and shipped within 30 days of the last sample being taken. The site should use the PBTC-047 FedEx account details, located on the PBTC member website. Ship all pharmacokinetic samples frozen and on dry ice, along with a completed Pharmacokinetics Sample Transmittal Form located on the PBTC-047 webpage to:

[name] Lab

Samples must be shipped from the site to the respective receiving laboratory within 30 days of last sample collection in order to receive cost reimbursement. The sample collection and shipping dates must be documented in the eCRF. Samples will be stored at this receiving laboratory, until additional details regarding the analyzing laboratory are available, which will be included in a forthcoming amendment.

9.2.4 Assay description including Site Performing Correlative Study

The purpose of this study is to evaluate and characterize the plasma pharmacokinetics of panobinostat in children with recurrent/progressive and non-progressed DIPG or H3K27M+ Thalamic DMG. 100 μ L of clinical sample in human plasma in Na heparin (or K₃EDTA) stored at -70°C \pm 10 is used in protein precipitation treatment (PPT). After sample treatment, the sealed plate is transferred onto auto-sampler of HPLC and then analyzed by an LC-MS/MS system. The dilution factors include 1/5, 1/20 and 1/50.

9.3 Pharmacodynamics: Cell-free DNA – Blood and Urine (Optional)

As an ancillary/exploratory study in consenting patients, blood and/ or urine will be collected to detect histone mutation status in cell-free DNA, via Microfluidic analysis of cell-free DNA.

9.3.1 Collection of Specimens

- Blood Sample
2-3 ml of serum peripheral blood for plasma will be collected on days 1 of courses 1, 2, 4, 6, and 12, pre-dose into K2-EDTA lavender top tubes.
- Urine Sample (No longer need to be collected as of version 8.0)
3-5 ml of urine will be collected on days 1 of courses 1, 2, 4, 6, and 12 pre-dose, preferably in the morning time.

9.3.2 Handling and Shipping of Specimens

- Blood Sample
At each time point, 2-3 ml of blood will be collected into appropriately labeled tubes containing K2-EDTA. Blood samples must be labeled with the PBTC accession number, protocol ID and date of collection. Samples should be batched for shipment once each patient's complete set has been collected and processed and shipped within 30 days of the last sample being taken. Blood samples should be shipped Monday through Wednesday via Federal Express Priority Overnight using the FedEx account information and transmittal form, located on the PBTC-047 webpage. Weekend deliveries are not permitted. Receipt and processing of biological materials will be recorded in ProtoLab, as

appropriate, by staff at the analyzing laboratory. The sites sending the materials must document sample collection and shipping dates in the eCRF.

During the sample collection and processing steps, the blood and plasma should be kept out of direct sunlight and unfiltered lab light. Upon collection of the blood cell-free DNA in K2-EDTA blood collection tubes, samples should be processed as soon as possible to minimize hemolysis and contamination due to DNA released from nucleated blood cells. Samples should be centrifuged at 800 x g for about 10 minutes at 4° C. The supernatants should then be transferred to new 1.5ml tubes, keeping the pellet for blood DNA extraction if needed. Then, the supernatants should be centrifuged at 16000 x g for about 10 minutes at 4° C. Aliquot the supernatants by 1ml and store at -80° C until use. Blood samples will be shipped overnight via Federal Express Monday through Wednesday with a 2-day supply of dry ice. Specimens will only be received Tuesday through Thursday.

Specimens should be sent to the following address:

[name]

[figure not shown]
Please notify [name] of a pending shipment along with the FedEx tracking number by telephone.

- Urine Sample (No longer collected as of version 8.0)

Collect 3-5 ml per time point, preferably in the morning to increase cfDNA concentration. Immediately freshly collected urine samples should be mixed with 0.5M EDTA pH 8.0 to a final concentration of 10mM EDTA (dilution 1/50), to inhibit possible nuclease found in urine. The samples should then be kept at -80°C until shipment. Urine samples must be labeled with the PBTC accession number, protocol ID and date of collection. Samples should be batched for shipment once each patient's complete set has been collected and processed and shipped within 30 days of the last sample being taken. Urine samples should be shipped Priority Overnight on dry ice via Federal Express Monday through Wednesday. Specimens will only be received Tuesday through Thursday.

Specimens should be sent to the following address:

[name]

Please notify [name] of a pending shipment along with the FedEx tracking number by telephone.

